6.3 MEASURES TO MINIMIZE BIAS: RANDOMIZATION AND BLINDING

Participants will be assigned to conditions by an algorithm programmed into the computer-based research portal. Randomization will utilize a permuted-blocks randomization scheme. Blocks of size 4 and 6 will be used. Assignments within blocks will be random but balanced among the two conditions and the order of the blocks (4 vs 6) also will be random. This procedure will ensure that the number of participants randomized to each condition will be equal, that any imbalance among the conditions at any point during the recruitment and randomization will be modest, and that it will be very difficult to guess the assignment of the next participant. Because the intervention and control materials are inherently different, participants and research staff cannot be blinded to assignment. To limit bias, primary outcome ascertainment (MRR-verified receipt of CRC screening within 6 months) will be conducted by clinic staff who abstract electronic health records without reference to group assignment; two abstractors will review each record and reconcile discrepancies, providing an additional safeguard against bias.

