9.2 SAMPLE SIZE DETERMINATION

To determine the adequate sample size for our study, we examined achieved power and treatment effects for a study examining the efficacy of a conceptually similar intervention with an equivalent data analysis plan. Specifically, Miller et al. developed a digital decision aid to help patients select a CRC screening test before a primary care appointment. Compared to controls, participants assigned to the decision aid were twice as likely to get screened at 6-month followup (30% [67/223] vs. 15% [34/227], difference=15%, 95% CI 7% to 23%; OR = 2.5). Follow-up analyses with only nonwhite participants continued to show a significant positive effect on screening (34% [33/98] vs. 19% [18/94], difference = 15%, 95% CI 6% to 25%; OR=1.79). Based on the similarity of this research to our own, we anticipate similar screening proportions in our study. To estimate power for the binomial logistic regression analysis on the primary outcome measure (MRR-verified CRC screening), we relied on the sub-analysis from Miller et al.'s data. Importantly, the OR in this analysis (1.79) is consistent with the average effect size of SMS-based interventions on health behaviors (OR=1.81). The G*Power 3.1 program was used to

determine that an odds ratio of 1.79, a two-tailed α error probability of 0.05, and 80% power requires a final sample size of 154 to detect an expected difference in screening rates of 15% at the 6-month follow-up. While unlikely, we will anticipate a conservative 20% attrition rate and set our sample size at 193 (n= 154 post-attrition).

As screening-related health beliefs are important secondary outcomes, we also examined power using treatment effects for screening self-efficacy from the Miller et al. decision aid study. Researchers found that participants in the intervention group reported significantly higher screening self-efficacy (n=223, M=3.89, SD=.84) than control participants (n=227, M=3.64, SD=1.00), $p=.004$. This difference is associated with a Cohen's $d = .27$. To detect a difference of this size in screening self-efficacy, our study will require a final sample size of 110 participants ($\alpha = 0.05$ two-tailed; power = .80). The 154 participants remaining in the analyses post-attrition will be sufficient to detect differences health beliefs across the two survey time points.

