9.4.3 ANALYSIS OF THE SECONDARY ENDPOINT(S)

Linear regression will be used to assess secondary outcomes. All analyses will control for any confounding variables not managed through randomization (i.e., group difference $p < .10$). For the secondary outcomes, we will conduct multiple imputation for any missing data using the procedures described for the primary outcome.

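### The secondary sample size of 110 for d = 0.27 is about a quarter of the 434 a two-arm comparison needs, so 154 participants are not sufficient for the health-belief outcomes (power about 38%)

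*Combined protocol and SAP*

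**What the plan says.** The second paragraph of Section 9.2 (Sample Size Determination) bases the secondary power statement on screening self-efficacy in a cited decision-aid trial. It compares intervention participants with controls: "n=223, M=3.89, SD=.84) than control participants (n=227, M=3.64, SD=1.00". It converts the difference to d = 0.27. With two-tailed alpha of 0.05 and 80% power it concludes that "our study will require a final sample size of 110 participants". The next sentence is the assurance: "The 154 participants remaining in the analyses post-attrition will be sufficient to detect differences health beliefs across the two survey time points". The 154 comes from the primary outcome, where "we will anticipate a conservative 20% attrition rate and set our sample size at 193 (n= 154 post-attrition").

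Section 9.1 states each scale hypothesis as a difference between arms in change from baseline to 6 months. On the analysis, Section 9.4.3 says "Linear regression will be used to assess secondary outcomes", with covariates limited to variables that differ between groups at p < .10. It does not list the baseline score as a covariate, and no baseline to follow-up correlation appears anywhere. Allocation is 1:1 (Section 6.3). The schema in Section 1.2 shows 128 participants, 63 and 65 per arm.

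**The concern.** The planning effect compares two independent groups, and so do the hypotheses. At d = 0.27, 110 participants means 55 per arm, which is far too few for 80% power on a contrast of that kind. The cited trial itself had 223 + 227 = 450 participants, and that size gives about 82% power at d = 0.27. About a quarter as many people cannot give nearly the same power for the same comparison.

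Section 3 presents the belief scales as tests of the causal mechanism or of possible moderation. A reader who accepts that they are adequately powered may take a null result as evidence against the Health Belief Model pathway. If the true difference is 0.27 SD, an unadjusted comparison at 154 would miss it about six times in ten.

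**Working it through.** **Inputs.** From Section 9.2: means 3.89 and 3.64; SDs 0.84 and 1.00; n = 223 and 227; two-sided alpha 0.05; power 0.80; 154 analysed. From Section 6.3: 1:1 allocation. From Section 1.2: 63 + 65 = 128. The plan gives no baseline to follow-up correlation (rho), so rho is varied below as an assumption.

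**Step 1: the effect size.** Pooled SD = sqrt[(222 × 0.84² + 226 × 1.00²)/448] = 0.924. Then d = (3.89 − 3.64)/0.924 = 0.2705, and the two-sample t test gives p = 0.0043. Both agree with the plan (0.27 and .004). The effect is a between-arm standardised difference.

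**Step 2: where 110 comes from.** The plan names no formula, but three calculations give 110 exactly:
- One-sample or paired t test at 0.27: n ≈ (1.960 + 0.842)²/0.27² = 107.7 by the normal approximation and 109.6 by noncentral t, so 110.
- Repeated-measures interaction (2 groups × 2 times) with f = d/2 = 0.135 and rho = 0.5: N = 110.
- Regression with f² = d² = 0.0729 in place of d²/4: N = 110.

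None of these fits the planned contrast. The first has no control arm. In the second, arms that are equal at baseline and 0.27 SD apart at follow-up have an interaction f of 0.27/4 = 0.0675, and that input gives N = 434; using 0.135 doubles the effect. In the third, the correct d²/4 = 0.018225 gives 433.

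**Step 3: the two-arm sample size.** n per arm = 2 × (1.960 + 0.842)²/0.27² = 215.3, so 216 (432 in total) by the normal approximation. Noncentral t gives 216.3, so 217 per arm and **434 in total**. The ratio 110/434 is 25%. With the plan's 20% attrition, 434/0.80 = 542.5, so 543 enrolled.

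**Step 4: power and detectable difference without baseline adjustment** (noncentral t, d = 0.27).

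| N | Per arm | Power | Detectable d at 80% |
|---|---|---|---|
| 110 | 55 + 55 | 28.9% | 0.54 |
| 154 | 77 + 77 | 38.4% | 0.45 |
| 128 | 63 + 65 | 32.9% | 0.50 |
| 102 | 51 + 51 | 27.2% | 0.56 |

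The last row assumes that the plan's 20% attrition applies to the schema's 128.

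**Step 5: the effect of using the baseline score.** With baseline adjustment the effective difference is d/sqrt(1 − rho²). With change scores it is d/sqrt[2(1 − rho)].

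| Assumed rho | Adjusted: N for 80% | Adjusted: power at 154 | Change score: N for 80% | Change score: power at 154 |
|---|---|---|---|---|
| 0.5 | 326 | 48.5% | 434 | 38.4% |
| 0.6 | 278 | 54.8% | 348 | 46.1% |
| 0.7 | 222 | 64.5% | 262 | 57.5% |
| 0.8 | 158 | 79.2% | 176 | 74.9% |

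Setting 434 × (1 − rho²) = 154 gives rho = 0.80 for adjustment. Setting 434 × 2(1 − rho) = 154 gives rho = 0.82 for change scores. For 110 to suffice, the same equations require 0.86 and 0.87.

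**The case against.** The strongest reply is that 38% is not a fixed property of this plan. The hypotheses concern change, the analysis section says only linear regression, and neither the dependent variable nor the use of the baseline score is specified. Depending on model and correlation, power at 154 could be lower than 38% (29% for change scores at rho = 0.3) or much higher (79% with adjustment at rho = 0.8). That is correct, so 38% must be labelled as the unadjusted figure, which also applies to change scores at rho = 0.5. It does not rescue the assurance. No correlation is assumed anywhere, and 154 reaches 80% only at about 0.80 or above.

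A second reply is that the sufficiency sentence refers to the two survey occasions and so may be a within-person claim, for which 110 is the right number. But d was taken from a between-arm comparison, and every scale hypothesis in Section 9.1 contrasts the arms. A within-person test answers none of them.

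Three smaller points stand. Section 9.2 makes its power statement for health beliefs and self-efficacy and does not mention knowledge. The 128 in the schema is the number allocated, not a count analysed. The primary outcome set the enrolment target of 193, so this error changes neither that target nor the primary analysis.

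**Conclusion.** The concern holds: the figure of 110 and the sufficiency statement are wrong as written. On the plan's own inputs (d = 0.27, two-sided 0.05, 80% power, 1:1 allocation) the unadjusted between-arm comparison needs 434, and 110 is about a quarter of that. This part rests on no outside assumption. Unadjusted power at 154 is about 38%, and the smallest difference detectable with 80% power is about 0.45 SD, some 1.7 times the planning effect (0.45/0.27).

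How far baseline adjustment closes the gap depends on a correlation the plan does not give. Over an assumed range of 0.5 to 0.7, adjusted power at 154 is about 49% to 64%, still well short of 80%. None of these figures allows for multiplicity across the several scale outcomes.

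**What to change.** In Section 9.2:
- Replace 110 with 434 in total (217 per arm), labelled as the requirement for an unadjusted two-arm comparison at d = 0.27.
- Delete the statement that 154 will be sufficient. Report unadjusted power of 38% at 154 and 33% if all 128 in the schema are analysed, with detectable differences of about 0.45 and 0.50 SD.
- If the baseline score is to be used, say so in Section 9.4.3, naming the dependent variable and the covariate. Give the assumed baseline to follow-up correlation in Section 9.2 with the resulting power, ideally over a range such as 0.5 to 0.8.
- State that null results on the belief scales will be read from confidence intervals, because the trial cannot reliably detect a difference of 0.27 SD.

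The cost is a few sentences and a less favourable statement about the secondary outcomes. Enrolment, procedures and the primary analysis are unaffected.

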9.3 POPULATIONS FOR ANALYSES

Because randomization carries the expectation of creating treatment groups equivalent with respect to known and unknown prognostic factors, removing randomized participants from the analysis runs the risk of tampering with this balance and introducing bias into the treatment comparisons. As a result, an intention-to-treat analytic approach will be followed such that all participants randomized into the study will be included in all analyses irrespective of protocol violations post randomization. Even with our best efforts, we can expect some missing data. For the primary outcome, missing data will be limited to cases where we are unable to complete an MRR review. Because we will have medical releases for all participants on our primary outcome, very little missing data is anticipated. For secondary measures, missing data will consist of those who fail to complete the 6-month follow-up survey. We will conduct an initial evaluation of missingness by performing a series of logistic regression analyses where the indicator of missing data is the outcome and potential explanatory variables (e.g., condition, screening status, demographic characteristics) serve as predictors. We will then use imputation to manage missing data.

9.4 STATISTICAL ANALYSES

9.4.1 GENERAL APPROACH

Binomial logistic regression will be the main analytic technique for the primary outcome (MRR-verified completion of a recommended CRC screening test). Logistic regression analyses will also examine treatment differences in type of screening received. For secondary outcomes, linear regression will be used. All analyses will control for any confounding variables not managed through randomization (i.e., group difference $p < .10$).

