8.1 ENDPOINT AND OTHER NON-SAFETY ASSESSMENTS

This individually randomized, remote trial evaluates a mobile, video+SMS colorectal cancer (CRC) screening education program versus a standard-materials control. All study activities are conducted virtually; no study-specific physical exams, imaging, or biospecimen collection occur. Outcome verification uses medical record review (MRR) and self-report.

Screening, eligibility, and enrollment

- **Eligibility confirmation window.** Up to 30 days prior to enrollment. Site staff confirm basic eligibility from clinic records (e.g., age, overdue for CRC screening per guidelines, active phone number).
- **Consent & MRR authorization.** Participants complete electronic informed consent and provide HIPAA authorization for MRR.
- **Baseline survey.** Immediately post-consent, participants complete a baseline questionnaire.
- **Randomization.** After baseline completion, participants are assigned to intervention or control.

Interventions begin (initial administration conditions)

- **Intervention arm.** Participants receive an SMS link to the curriculum hub and proceed through brief, pre-recorded videos with tailored branches, followed by a post-education screening assistance (PESA) text sequence.
- **Control arm.** Participants receive text messages, some with links to standard educational materials via SMS. A working mobile number and ability to receive texts are required for delivery; there are no in-person or group sessions.

Measures and assessments (non-safety)

Baseline (pre-randomization)

- Demographics and contact details (mobile number required for delivery).
- CRC screening history (ever screened; modality and timing if applicable).
- Psychosocial measures (e.g., CRC knowledge; perceived risk/severity; perceived benefits/barriers for stool tests and colonoscopy; medical trust; self-efficacy).

During intervention (process/dose)

- Platform telemetry: timestamps for each SMS, link launches, chapter/video opens (percent viewed), assessment completions, participant replies (including keyword confirmations), and time in the assistance stream. These are used for exposure/dose summaries and adherence monitoring (not safety).

Follow-up (primary outcome window)

- **Primary outcome ascertainment:** Receipt of any guideline-concordant CRC screening within 6 months post-randomization, verified by MRR (test type, date, and result if available) and self-report.

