9.4.5 BASELINE DESCRIPTIVE STATISTICS

All analyses will control for any confounding variables not managed through randomization (i.e., group difference $p < .10$).

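### Covariates are chosen by a baseline test at p < .10, so chance imbalance sets the primary model; a short fixed list would be modestly more efficient and settled in advance.

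*Combined protocol and SAP*

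**What the plan says.** Section 9.4.1 fixes the form of the primary analysis: "Binomial logistic regression will be the main analytic technique for the primary outcome". The covariate rule follows: "All analyses will control for any confounding variables not managed through randomization (i.e., group difference", the bracket closing with p < .10. Section 9.4.3 repeats the rule for the secondary linear models. Section 9.4.5, which should describe baseline reporting, holds only the same sentence: "All analyses will control for any confounding variables not managed through randomization".

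No section fixes a covariate for the primary model:

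- Section 9.4.2, on the primary endpoint, deals only with missing data. It names age, income and health insurance as predictors for imputation, not as model covariates.
- Section 6.3 describes permuted blocks of 4 and 6 and names no stratification factor, so the design supplies no covariate.
- Section 8.1 lists baseline data that include "CRC screening history (ever screened; modality and timing if applicable" and the psychosocial scales, but gives them no role in the primary model.
- Neither the candidate variables nor the baseline test is stated.

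Section 9.3 supports intention-to-treat with the words "Because randomization carries the expectation of creating treatment groups equivalent with respect to known and unknown prognostic factors".

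**The concern.** The rule defines a confounder by its difference between arms alone. Relation to the outcome plays no part. In a properly randomised trial a baseline difference arises by chance, so its p-value says nothing about whether adjustment is worthwhile. A useless variable can enter and a good predictor is usually left out.

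Three things are at stake. First, the primary model, its odds ratio and its p-value are settled only after baseline data have been compared by arm. The candidate list is open, and Section 6.3 says research staff cannot be blinded. Second, the precision available from prognostic covariates is mostly given up. Third, the odds ratio is non-collapsible: its value changes when a prognostic covariate is added, even with perfect balance. What is estimated therefore depends in part on what happens to be selected.

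**Working it through.** **1. The plan's own figure.** Section 9.2 plans on "34% [33/98] vs. 19% [18/94], difference = 15%, 95% CI 6% to 25%; OR=1.79" and says that "a two-tailed α error probability of 0.05, and 80% power requires a final sample size of 154". The attrition step reproduces: 154/0.8 = 192.5, so 193. The 154 does not reproduce for two arms at 34% and 19%:

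n per arm = [1.96√(2 × 0.265 × 0.735) + 0.8416√(0.34 × 0.66 + 0.19 × 0.81)]² / 0.15² = (1.223 + 0.518)² / 0.0225 ≈ 134.7

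That is 135 per arm, 270 in total. Power is about 56% with 77 per arm and 49% with the 63 and 65 in the Section 1.2 flow diagram. This is a separate issue, but it sets the base for the power figures below.

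**2. Chance of selection.** With k independent candidates tested at 0.10, P(at least one enters) = 1 − 0.9^k and the expected number is 0.1k.

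| k | P(at least one) | Expected number |
|---|---|---|
| 5 | 41% | 0.5 |
| 10 | 65% | 1.0 |
| 15 | 79% | 1.5 |
| 20 | 88% | 2.0 |

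The documents do not give k. About 15 is reasonable: severity, susceptibility, benefits and barriers for each of two tests, knowledge, self-efficacy and trust make nine scores, and demographics and screening history come on top. Correlated scales would lower these probabilities.

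With three prognostic factors, none enters with probability 0.9³ = 73%, at least one with 27%, and all three with 0.1³ = 0.1%.

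**3. Power, with continuous covariates.** Simulation of 6,000 trials per scenario, with 34% vs 19%, 10 independent candidates and 3 of them prognostic. The log odds ratio per SD is assumed.

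| N | Log OR per SD | Unadjusted | p < .10 rule | Three fixed |
|---|---|---|---|---|
| 154 | 0.3 | 53% | 53% | 55% |
| 154 | 0.5 | 56% | 57% | 62% |
| 154 | 0.8 | 55% | 56% | 67% |
| 128 | 0.3 | 49% | 47% | 51% |
| 128 | 0.5 | 48% | 47% | 52% |
| 128 | 0.8 | 48% | 48% | 59% |

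The rule stays within about 1 point of no adjustment. Under the null it rejected in 4.1% to 4.8% of trials, and the fixed model in 4.7% to 5.3%.

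**4. Power, with covariates like those available.** Assume normal age, 50% ever screened, 85% insured, and 5,000 trials at N = 154. With odds ratios of 1.2 per SD, 1.5 and 1.5, the fixed model moves power from 57% unadjusted to 58%. With 1.3, 2 and 2 it moves from 54% to 57%. With 1.3, 3 and 2 it moves from 55% to 59%. Measured against the p < .10 rule, the gain is about 1 to 5 points.

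**5. Shift in the odds ratio.** The unadjusted target is (0.34/0.66)/(0.19/0.81) = 2.20. Take two prognostic factors, with log odds ratios from 0.5 and 0.4 per SD up to 0.9 and 0.7. The adjusted target is 2.26 to 2.43 with one in the model and 2.3 to 2.6 with both. Under the rule neither enters with probability 0.9² = 0.81, one with 2 × 0.1 × 0.9 = 0.18, and both with 0.1² = 0.01. Weighting the log odds ratios gives an average of 2.21 to 2.24. Fitted small samples average about 2.3.

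**6. Events available.** The overall rate is (0.34 + 0.19)/2 = 26.5%. That gives 0.265 × 154 ≈ 41 events, or 0.265 × 128 ≈ 34.

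**The case against.** The strongest reply is that the rule does little harm. It costs about a point of power at most relative to no adjustment, error rates are held, and the better model gains only a few points in a trial that would still be far below 80%. That stands, and it limits the weight of this point.

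The documents also do not show that the natural covariates are strong. Section 2.2 links younger age and inconsistent insurance to lower screening without giving a strength. No section says that past screening predicts uptake among men who are all non-compliant at entry. For a 50/50 factor, log odds ratios of 0.9 and 0.7 per SD correspond to odds ratios of 6.0 and 4.1, so gains of about 10 points need an assumption the documents do not support.

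Stronger readings that a reader might infer should be set aside:

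- *The rule inflates false positives.* Applied mechanically, it does not.
- *The reported odds ratio will drift to 2.3 to 2.6.* That range belongs to a model holding both prognostic covariates, which the rule reaches in about 1% of trials.
- *Section 9.3 concedes that every baseline difference is chance.* It speaks of an expectation of equivalence, in support of intention-to-treat. The conclusion about chance follows from randomisation, not from that sentence.

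None of this defends the rule as a way of choosing covariates.

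**Conclusion.** The point holds as a recommended change. The text is clear: one rule, stated three times, governs the primary model, and no covariate is fixed. Selection at about 0.10 per variable follows from randomisation. The chance of at least one entry runs from 41% to 88% for 5 to 20 candidates and assumes independence.

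The size of the loss is less certain. It is about 1 to 5 power points at 154 for plausible binary and continuous factors, and about 10 only under strong assumed prognosis. Fixed covariates would not rescue the sample size in any scenario examined. The average movement of the odds ratio under the rule is small. The firmer reason to act is that the primary model should be known before the data are compared by arm.

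**What to change.** Delete the p < .10 rule in Sections 9.4.1, 9.4.3 and 9.4.5, and replace it as follows.

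- **Primary model:** arm plus a short list of baseline covariates thought to be prognostic, for example age, health insurance and ever screened, included whatever the observed balance. Consider income, since Section 9.4.2 already uses it. Confirm that insurance is recorded at baseline, because Section 8.1 lists only demographics.
- **Secondary linear models:** the outcome's own baseline score plus the same covariates. Section 9.1 frames these outcomes as change from baseline, so removing the rule without a replacement would leave a gap.
- **Missing covariates:** Section 2.3.1 lets participants skip questions. State one simple method, for example a mean or a missing category set without regard to arm, and put the same covariates in the imputation model.
- **Reporting:** the unadjusted model as a sensitivity analysis; the standardised risk difference with its confidence interval beside the odds ratio, since Section 9.2 plans on a 15-point difference; baseline balance described without tests.

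Timing matters. Sections 2.1 and 4.1 are partly in the past tense and Section 1.2 shows 63 and 65 randomised. The list must be fixed and dated before outcomes are compared by arm. If that comparison has already been made, the report should say the covariates were chosen afterwards.

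The cost is some SAP wording and a few degrees of freedom against about 34 to 41 expected events, so the list must stay short. The adjusted odds ratio will be conditional on the covariates, which is why the risk difference belongs beside it.
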